- Also, where two or more consecutive concentrations are BQL towards the end of a profile, the profile will be deemed to have terminated and therefore any further quantifiable concentrations will be set to missing for the calculation of the PK parameters unless it is considered to be a true characteristic of the profile of the drug.

Individual Concentration vs. Time Profiles

- Individual concentrations will be plotted utilizing actual sampling times.
- The terminal point selections will be indicated on a semi-logarithmic plot.

Average Concentration vs. Time Profiles

- The average concentration profiles will be graphed using scheduled (nominal) sampling times.
- The average concentration profiles will be graphed using arithmetic average concentrations.
- The pre-dose average concentration for single-dose data from non-endogenous compounds will be set to zero. Otherwise, only quantifiable concentrations will be used to calculate average concentrations.
- Concentrations at a sampling time exceeding the sampling time window specified in the protocol, or $\pm 10\%$, will be excluded from the average concentration profiles.
- Concentrations excluded from the mean calculation will be documented in the final study report.
- A concentration average will be plotted for a given sampling time only if 2/3 of the individual data at the time point have quantifiable measurements that are within the sampling time window specified in the protocol or $\pm 10\%$. An average concentration estimated with less than 2/3 but more than 3 data points may be displayed on the mean concentration plot if determined to be appropriate and will be documented within the final study report.

Treatment of Outliers during Pharmacokinetic Analysis

Application of this procedure to all PK analyses is not a requirement. Rather, this procedure provides justification for exclusion of data when scientifically appropriate. This procedure describes the methodology for identifying an individual value as an outlier for potential exclusion, but does not require that the value be excluded from analysis. The following methodology will not be used to exclude complete profiles from analysis.

Data within an Individual Profile

A value within an individual profile may be excluded from analysis if any of the following criteria are met:

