- For PK profiles during multiple dosing, the concentration of the pre-dose sample exceeds all measured concentrations for that individual in the subsequent post-dose samples.
- For PK profiles during single dosing of non-endogenous compounds, the concentration in a pre-dose sample is quantifiable.
- For any questionable datum that does not satisfy the above criteria, the profile will be evaluated and results reported with and without the suspected datum.

Data between Individual Profiles

1. If $n < 6$, then the dataset is too small to conduct a reliable range test. Data will be analyzed with and without the atypical value, and both sets of results will be reported.
2. If $n \geq 6$, then an objective outlier test will be used to compare the atypical value to other values included in that calculation:
 - a. Transform all values in the calculation to the logarithmic domain.
 - b. Find the most extreme value from the arithmetic mean of the log transformed values and exclude that value from the dataset.
 - c. Calculate the lower and upper bounds of the range defined by the arithmetic mean $\pm 3*SD$ of the remaining log-transformed values.
 - d. If the extreme value is within the range of arithmetic mean $\pm 3*SD$, then it is not an outlier and will be retained in the dataset.
 - e. If the extreme value is outside the range of arithmetic mean $\pm 3*SD$, then it is an outlier and will be excluded from analysis.

If the remaining dataset contains another atypical datum suspected to be an outlier and $n \geq 6$ following the exclusion, then repeat step 2 above. This evaluation may be repeated as many times as necessary, excluding only one suspected outlier in each iteration, until all data remaining in the dataset fall within the range of arithmetic mean $\pm 3*SD$ of the log-transformed values.

Reporting of Excluded Values

Individual values excluded as outliers will be documented in the final report. Approval of the final report will connote approval of the exclusion.

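### SAP 9.3.1: with six or more values, a 3-SD test can drop a Cmax or AUC value on size alone, and the primary ratio with that value kept in need not be reported

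*SAP*

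**What the plan says.** The rule is in SAP 9.3.1, under the heading on treatment of outliers. Its preamble makes use of the procedure optional. It says that "this procedure provides justification for exclusion of data when scientifically appropriate" and that the method "does not require that the value be excluded from analysis". It also sets one limit: "The following methodology will not be used to exclude complete profiles from analysis".

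For comparisons between subjects, the treatment depends on the number of values:

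- **Fewer than six:** "Data will be analyzed with and without the atypical value, and both sets of results will be reported".
- **Six or more:** an objective test is used to "compare the atypical value to other values included in that calculation". The values are logged, the most extreme one is set aside, and it is compared with the mean ± 3 SD of the rest. If it falls outside, "then it is an outlier and will be excluded from analysis". The step may be repeated while at least six values remain.

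Within a single profile, a value may be dropped under listed criteria, for example when, after a single dose, "the concentration in a pre-dose sample is quantifiable". For a questionable value that meets no listed criterion, "the profile will be evaluated and results reported with and without the suspected datum".

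Excluded values are to be documented in the final report, and approving the report counts as approving the exclusion. SAP 9.1 requires listings of everything in the database. SAP 8 and Protocol 10.3 define the PK set as all data from every dosed subject. SAP 9.3.2, which gives the primary mixed model, does not mention outliers and says only that further analyses may be done.

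**The concern.** The test is prespecified, but its use is not. Someone decides after seeing the data which value looks atypical, and the two wordings leave open whether a flag must be acted on. Two analysts could follow the SAP, one keeping a flagged Cmax and the other removing it, and report different primary ratios. The study is open-label, and steps 2a to 2e ask for no assay, sampling or dosing cause. The condition in the preamble about scientific appropriateness is undefined.

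The dual reporting that would settle this is required below six values and for a questionable value within a profile. It is missing from the one branch that governs the primary analysis. The Protocol synopsis says the results will inform dose selection for later tablet studies. An occasional poorly absorbed tablet is something such a study should show, and the rule can take it out of the ratio because it is extreme.

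**Working it through.** **Inputs.** SAP 7 plans about 24 enrolled so that at least 20 complete, so the branch for six or more applies. SAP 9.3.1 gives the 3-SD leave-one-out rule; SAP 9.3.2 gives the mixed model and 90% CI. The plan gives no figure for the effect of the rule, and the variability behind the sample size is blacked out. I therefore assume between/within-subject log-SDs of 0.2/0.15, 0.3/0.2 and 0.4/0.25. Results below are in that order. The simulations used 20 subjects, six sequences, fixed treatment and period, random subject and 4,000 runs per case. Every dataset was tested and every flag acted on, so the effects are upper limits.

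**1. How often a valid value is flagged.** In clean log-normal data the left-out deviation, in SDs of the others, follows √(1 + 1/(n−1)) × t on n−2 df.

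- n = 20: limit 3/√(1 + 1/19) = 2.924 on 18 df; two-sided p = 0.00906 per value; × 20 = 0.181. This sum is an upper bound; simulation gave 0.179.
- n = 24: bound 0.183, simulated 0.177.

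This needs no variability assumption beyond log-normality. Testing three treatments separately would give 1 − (1 − 0.18)³ = 0.45 if they were independent. Because the same subjects are in each, the simulated figure is 40–43% of trials per parameter.

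**2. Effect in clean data.** 90% CI coverage goes from 0.899, 0.905, 0.901 to 0.890, 0.894, 0.889, a loss of about 1 point.

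**3. One genuine low value.** One fasted-tablet value among 20 is 80% low and everything else is equal. Kept in, it gives a ratio of 0.2^(1/20) = 0.923. Removed, the ratio returns to about 1.00, and 1/0.923 = 1.083, a move of about 8%. The rule flags it in 1.00, 0.91 and 0.67 of runs. Upper/lower CI limit ratios are 1.31, 1.36, 1.41 with the value kept and 1.18, 1.25, 1.34 under the rule. A low capsule value works the other way: the ratio is about 1.084 kept, and 1.00, 1.01, 1.03 under the rule.

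**4. Assumed failures.** Here 5% of fasted-tablet values fail. Coverage is scored against the population mean log ratio including failed doses (80% loss: 0.05 × ln 0.2 = −0.080, ratio 0.92).

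| Assumed loss | Coverage, no rule | Coverage, rule applied |
|---|---|---|
| 80%, single values removable | 0.780, 0.821, 0.862 | 0.504, 0.661, 0.783 |
| 80%, value kept if Cmax and AUC are both flagged | 0.780–0.860 | 0.775–0.850 |
| 70%, Cmax only | 0.836, 0.869, 0.871 | 0.662, 0.804, 0.835 |
| 60%, Cmax only | 0.865, 0.884, 0.880 | 0.770, 0.856, 0.862 |
| 50%, single values removable | 0.877, 0.895, 0.891 | 0.843, 0.874, 0.876 |

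In the first row the ratio moves from 0.92 to 0.988, 0.980, 0.961. In the second it is 0.924–0.936. If the first case is scored against the ratio for non-failed doses (1.00), the rule raises coverage from 77–81% to 84–87%.

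**The case against.** The sponsor has good replies.

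- **Wording.** The preamble introduces the whole method, so step 2e can be read as what follows once the method is invoked. That makes the conflict mild, but the text should still say so.
- **Transparency.** Exclusions are documented and data are listed, so nothing is hidden and a reader could refit the model. This stands. What is missing is a requirement that the report show the result.
- **Analysis set.** The PK set is all data and the model section names no outlier step, so an all-values primary analysis is a possible reading. The text does not say whether the outlier rule overrides the set definition, so this does not settle the point.
- **Scope.** Cmax and AUC are not named in the rule. However, the rule covers any calculation between profiles and works on the log scale, and SAP 9.1 treats these parameters as log-normal.
- **Dropping a quantifiable pre-dose value.** This also carries no dual reporting, but it rests on an identifiable reason and is not part of the concern.
- **Comparing between subjects.** A within-subject test might suit a crossover better, but that is a preference. At 0.4/0.25 a 50% loss is 1.47 total SDs but 1.96 SDs of the within-subject difference, so the SAP's test would flag fewer such values.

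A reader might infer that the rule hides formulation failures and cuts 90% CI coverage to 50–78%. The documents do not support that. It needs failure rates and sizes that appear nowhere in them, every flag acted on under an optional procedure, a reading of the bar on whole-profile exclusion that lets Cmax and AUC of one profile go singly, and a target that includes failed doses. With the protective reading the harm from a whole-profile loss nearly disappears; with the other target the direction reverses.

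**Conclusion.** The concern holds, at minor to moderate severity. At the planned size a primary value can be removed for its size alone, the SAP is inconsistent on whether it must be, and the ratio with it kept in need not be reported.

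The 18% flag rate rests only on log-normality; the 40% figure also assumes that each treatment is tested. Average harm in clean data is slight. The practical exposure is a single genuine extreme value. The 8% figure assumes an 80% low value among 20 and that it is both flagged and removed; the CI widths also depend on the assumed SDs. The visible text sets no equivalence limit, so no change in a pass/fail conclusion is claimed.

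**What to change.** Four wording changes in SAP 9.3.1 and 9.3.2:

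1. State that the primary mixed model uses all Cmax and AUC values in the full analysis set, except those excluded for a documented cause listed before data review, such as a sample or assay error.
2. Use steps 2a to 2e only to select values for a sensitivity analysis.
3. Report the ratio and 90% CI with and without any flagged value at six or more values, as is already required below six.
4. Reword step 2e to agree with the preamble.

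The cost is SAP text and one extra model run per affected parameter; design and sample size do not change. The downside is a wider primary CI when a genuine extreme value stays in, as step 3 of the working shows. Keeping all values does not restore 90% coverage when failures occur in one arm only (78–86% in the assumed 80% case), which is why both results should be shown.

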9.3.2 Pharmacokinetic Parameter Estimation

The primary parameters for analysis, C_{max} , $AUC(0-\infty)$, $AUC(0-t_{last})$, and t_{max} of LY3202626, will be evaluated to delineate relative bioavailability and food effects.

The following comparisons will be interests of statistical analysis of PK parameters:

- relative bioavailability: LY3202626 T1-12 fasted (test) versus LY3202626 R fasted (reference)
- food effect: LY3202626 T1-12 fed (test) versus LY3202626 T1-12 fasted (reference).

Log-transformed C_{max} and AUC estimates will be evaluated in a linear mixed -effects model with fixed effects for dose administration and period and a random effect for subject. The ratio of geometric least squares means and corresponding 90% CI will be presented for LY3202626 T1-12 versus LY3202626 R for analysis of relative bioavailability, and LY3202626 T1 -12 administered with a high-fat meal versus LY3202626 T1-12 administered fasted for the analysis of the food effect. One model will be used for the assessment of relative bioavailability and the effect of food.

The t_{max} will be analyzed non-parametrically for the same comparisons stated above. Median of differences and approximate 90% CI for the median of differences will be calculated. P-values will also be calculated using a Wilcoxon signed rank test.

Additional analyses may be performed if deemed necessary.

Example SAS code:

```
proc mixed data=test covtest alpha=0.1;
  class treatment period subject;
  model log_pk = treatment period / ddfm=kr alpha=0.1;
  random subject;
  lsmeans treatment / pdiff cl alpha=0.1;
  ods output lsmeans=lsmeans;
  ods output diffs=diffs;
  ods output covparms=cov;
run;
```

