3.1. Study Rationale

This study will explore the rate and extent of LY3202626 absorption when administered using a pilot tablet formulation using the CCI [REDACTED] as compared to the drug-in-capsule formulation using the CCI [REDACTED] that was used in previous studies. A 12-mg dose is the highest dose currently being evaluated in Phase 2 studies, and is projected to be the highest dose to be evaluated in Phase 3 studies. The effect of a high fat meal on the rate and extent of LY3202626 absorption will also be explored. The results of this study will be used when selecting doses for future clinical evaluations using a tablet formulation of LY3202626 and to understand whether the tablet formulation may be administered without regard to food. The change from baseline of amyloid beta (A β) isoforms (A β 1-40 and A β 1-42) will be evaluated at the 12-mg LY3202626 dose level for both tablet and capsule formulations.

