8. DEFINITION OF ANALYSIS POPULATIONS

The "Safety" population will consist of all enrolled subjects, whether or not they completed all protocol requirements.

The PK analyses will be conducted on the full analysis set. This set includes all data from all subjects who received at least one dose of LY3202626.

The "Pharmacodynamic" population will consist of all subjects who received at least one dose of study drug and have evaluable PD data.

All protocol deviations that occur during the study will be considered for their severity/impact and will be taken into consideration when subjects are assigned to analysis populations.

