11. CHANGES FROM THE PROTOCOL SPECIFIED STATISTICAL ANALYSES

There were no changes from the protocol specified statistical analyses.

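### Does the single residual variance shared by capsule fasted, tablet fasted and tablet fed make the planned 90% confidence intervals unreliable?

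*SAP*

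**What the plan says.** SAP section 9.3.2 fits log-transformed Cmax and AUC with "fixed effects for dose administration and period and a random effect for subject", and adds that "One model will be used for the assessment of relative bioavailability and the effect of food". The example code matches the text: the model line is "model log_pk = treatment period / ddfm=kr alpha=0.1", and the only covariance specification is "random subject". Nothing in the code lets the residual variance differ by treatment. Both 90% intervals, tablet fasted against capsule fasted and tablet fed against tablet fasted, come from this one fit.

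Protocol section 10.3.2.2 specifies the same model, so the statement in SAP section 11 that "There were no changes from the protocol specified statistical analyses" is correct here. The PK analysis set is broad: "This set includes all data from all subjects who received at least one dose of LY3202626". No check of the variance assumption is named. The only opening is that "Additional analyses may be performed if deemed necessary".

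**The concern.** A high-fat meal could plausibly change how variable absorption is from one occasion to the next. A model with a random intercept and one residual variance cannot represent that. It averages the three within-subject variances and applies the average to both contrasts. Nobody is fed in the primary comparison, yet the fed arm contributes a third of the pooled variance when all arms are equal, and more if the fed arm is noisier. With a fed SD 1.5 times the fasted SD, its share is 2.25/(2 + 2.25) = 53%.

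The 90% interval is the stated uncertainty for the primary ratio and for the food-effect ratio. Protocol section 3.1 says the results will guide dose selection and help "to understand whether the tablet formulation may be administered without regard to food". A food-effect interval that is too narrow would overstate certainty on that question. A less variable fed arm would make the primary interval too narrow. Leaving any alternative model until the data are in hand is also weaker than naming it beforehand.

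**Working it through.** **Inputs.** From the documents: six sequences, three periods, each treatment once per subject, at least 20 completers from about 24 enrolled (SAP sections 5 and 7), Kenward-Roger degrees of freedom and 90% intervals (SAP section 9.3.2). Assumed: the within-subject variances vA (capsule fasted), vB (tablet fasted) and vC (tablet fed). The precision calculation and the earlier capsule food result are blacked out, so the plan's own precision figure cannot be reproduced and the variances must be taken over a range.

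**Degrees of freedom, 20 completers.** Pooled model: 60 observations − 20 subjects − 2 treatment − 2 period terms = 36. Two-arm model for one contrast: 40 − 20 − 1 − 2 = 17.

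**Closed form.** With complete data the model gives either contrast the variance 2 × (vA + vB + vC)/3 ÷ n. The true variances are (vA + vB)/n for the primary contrast and (vB + vC)/n for the food effect. With vA = vB = 1 and vC = r, model variance divided by true variance is:

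- primary: (2 + r)/3
- food effect: 2(2 + r)/(3(1 + r))

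**Coverage.** Simulated with 400,000 trials per setting, n = 20, equal fasted variances:

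| Fed/fasted SD ratio | r | Variance ratio, primary / food | Coverage of 90% CI, primary / food |
|---|---|---|---|
| 0.5 | 0.25 | 0.750 / 1.200 | 84.6% / 92.6% |
| 0.75 | 0.5625 | 0.854 / 1.093 | 87.2% / 91.4% |
| 1 | 1 | 1 / 1 | 90.0% / 89.9% |
| 1.25 | 1.5625 | 1.188 / 0.927 | 92.6% / 88.7% |
| 1.5 | 2.25 | 1.417 / 0.872 | 94.7% / 87.6% |
| 2 | 4 | 2.000 / 0.800 | 97.7% / 85.9% |

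A ratio of 2 means a four-fold variance difference.

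**Direction.** The two intervals err in opposite directions here because the fasted variances were set equal. If they differ, that pattern can fail. Variances (vA, vB, vC) of (2, 1, 2) give 91.6% and 91.7%, both too high; (1, 2, 1) give 87.9% and 87.9%, both too low.

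**Size on the ratio scale.** Assume a fasted log-scale SD of 0.20 and compare the planned model with one that has an unstructured covariance by treatment. The factor from point estimate to upper limit is exp(half-width):

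- SD ratio 0.5, primary: exp(0.0920) = 1.096 against exp(0.1084) = 1.114
- SD ratio 0.75, primary: exp(0.0981) = 1.103 against exp(0.1084) = 1.114
- SD ratio 1, primary: exp(0.1060) = 1.112 against exp(0.1084) = 1.114
- SD ratio 1.5, primary: exp(0.1261) = 1.134 against exp(0.1083) = 1.114
- SD ratio 1.5, food effect: exp(0.1261) = 1.134 against exp(0.1379) = 1.148

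These limits move by two percentage points or less. A larger SD would give larger shifts.

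**Price of separating the error terms.** The relative error of an estimated SE is roughly 1/√(2 × df): 1/√72 = 11.8% on 36 df and 1/√34 = 17.1% on 17 df. The simulation adds the bias from pooling and gives these root mean square errors of the SE:

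| SD ratio | Pooled, primary / food | Two-arm fit, either contrast |
|---|---|---|
| 0.5 | 18% / 16% | 17% |
| 0.75 | 14% / 13% | 17% |
| 1 | 12% / 12% | 17% |
| 1.25 | 15% / 12% | 17% |
| 1.5 | 23% / 14% | 17% |
| 2 | 44% / 16% | 17% |

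For the food effect, the pooled SE is the closer one at every ratio tried. For the primary contrast it is closer from 0.75 to 1.25, about equal at 0.5, and worse at 1.5 and 2, where it errs towards an interval that is too wide.

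**The case for a change.** The best case for changing the model is that it would be cheap and would restore coverage. An unstructured covariance by treatment held 89.5% to 90.5% in simulation, and two-arm fits gave about 90% in every setting. If variances are in fact equal, the unstructured model costs only about 2.3% in log-scale width (0.1084 against 0.1060). Unequal residual noise is also not the only trigger. If subjects respond differently to the meal, that interaction enters the pooled residual. With equal within-subject SDs of 0.20 and an assumed interaction SD of 0.20, coverage was 94.1% (primary) and 88.2% (food effect). The SAP must be signed before first dosing, so an alternative could still have been named in advance.

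The algebra and coverage figures stand, and so does the remark that no check is prespecified. What does not follow is that the planned model is wrong. Every unequal-variance setting above is an assumption, and the earlier data that might have supported pooling are blacked out. Average coverage is also not the only criterion: an SE on about 17 degrees of freedom varies more from trial to trial, which offsets the bias removed when heterogeneity is mild. Replacing the model would estimate six covariance parameters from about 20 subjects and create a departure from the protocol where none exists.

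**Conclusion.** No change is needed. The common residual variance is a real modelling assumption, but it is a conventional one, it is stated identically in protocol and SAP, and it is efficient when roughly true. For 20 completers, equal fasted variances and fed/fasted SD ratios from 0.75 to 1.25, the coverage error is less than 3 points (primary) and less than 2 points (food effect), and pooling gives the more accurate SE. For more extreme ratios coverage ran from 84.6% to 97.7%, but nothing readable indicates that such ratios apply. No equivalence margin is readable either, so the consequence is somewhat misstated precision in a study described as exploring absorption, with no pass/fail result shown to change.

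If the data show clearly unequal spread, an analyst can report a contrast-specific fit beside the planned one as an additional analysis, which SAP sections 3 and 9.3.2 already allow and which would be identified in the study report. The planned primary result would stand unchanged. The judgement rests on the assumed range of variance ratios and would be weaker if the blacked-out data showed a large effect of food on variability.
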